Study Design: This study is an open-label, randomized, multi-center Phase II proof-of-concept study with a dose confirmation component (dose confirmation component now completed) to assess whether patients with platinum sensitive recurrent p53 mutated high grade serous ovarian cancer (HGSOC) will benefit from treatment with APR-246 in combination with a carboplatin/pegylated liposomal doxorubicin (PLD) chemotherapy regimen. All patients will have pre-screening immunohistochemistry (IHC) test that will determine p53 status and therefore the suitability to participate in this study. Patient's archived sections from the original tumor sample will be reviewed by a gynecological pathologist to confirm the diagnosis of HGSOC, and positive staining for p53. Patients without positive p53 staining will not be included. Patients will be randomly assigned in a 1:1 ratio to receive either: 
• Arm A: APR-246 with the carboplatin/PLD chemotherapy regimen,• Arm B: Carboplatin/PLD chemotherapy alone. The trial will enroll up to a maximum of 400 patients with positive IHC staining for p53. A CT scan/MRI using RECIST v1.1 criteria will be performed at pre-treatment, after 2 cycles (8 weeks), 4 cycles (16 weeks), and after the last cycle (24 weeks).	

At subsequent follow-up visits, tumor assessments by CT scan/MRI will be performed 2 months (\pm 2 weeks) after the end of treatment visit and every 3 months (\pm 2 weeks) thereafter, until the documented disease progression, as determined by the Investigator at each site and defined by RECIST v1.1.

Optional frozen/fixed core biopsies will be undertaken after randomization, but prior to any infusion, for all patients and on day 3 in APR-246 patients.

Objectives, Endpoints and Study Treatment:

Objectives:

Primary Objective:

- To assess the efficacy of a combined APR-246 and carboplatin/PLD chemotherapy regimen in patients with platinum sensitive recurrent HGSOC with mutated TP53.

Secondary Objective:

- To assess the safety profile of the combined APR-246 and carboplatin/PLD chemotherapy regimen compared with carboplatin/PLD chemotherapy regimen alone.
- To evaluate potential biomarkers.
- To assess the biological activity in tumor and surrogate tissues.
- To compare quality of life of patients treated with these regimens.

Endpoints:

Primary Endpoint

- Progression-free survival (PFS) based on Blinded Independent Central Review (BICR) is the primary endpoint and is defined as the number of days from the date of randomization to the date of objective disease progression or relapse (according to RECIST v1.1 only) or death due to any cause, whichever occurs first. If neither event occurs, PFS will be censored at the date of the last evaluable tumor assessment. Symptomatic deterioration is not objective disease progression.

Secondary Endpoints

- Best overall response and overall response rate (according to RECIST v1.1 and GCIG criteria)
- Duration of response (complete or partial response)
- PFS by assessment of CA-125 (according to GCIG Criteria)
- Overall survival
- Safety profile based on AEs and laboratory assessments
- Evaluation of biomarkers and tumor activity based on CA-125
- Quality of Life assessment using EORTC Ovarian (QLQ-30 and QLQ-OV28) and the Functional Assessment of Cancer Therapy-Ovarian (FACT-O)

Tumor response data will be summarized at each tumor assessment cycle using the following response categories: Complete Response (CR), Partial Response (PR), Stable Disease (SD), Progressive Disease (PD) and Non-Evaluable (NE). Best overall response for a patient is the best response recorded from the start of the treatment until disease progression or death. Best overall response will be summarized as the number (%) of patients in each category of response (CR, PR, SD, PD, and NE). PR and CR must be confirmed by a repeat assessment at least 28 days after the criteria are first met for the response to be considered a PR or CR.

The overall response rate is defined as the percentage of patients with a confirmed response of CR or PR in a given population.

The duration of response (confirmed CR or PR) is defined as the number of days from the date of initial response (not the confirmation date) to the date of objective disease progression or death due to any cause, whichever occurs first. If neither event occurs, duration of response will be censored at the date of the last evaluable tumor assessment. Symptomatic deterioration is not objective disease progression.

Overall survival (OS) is defined as the number of days from the date of randomization to the date of death. In the event of no death, overall survival will be censored at the last known alive date.

Study Treatment:

Arm A (APR-246). Patients will receive a fixed dose of 4.5 g APR-246 (1.5 g of the dose during first 45 minutes followed by 3 g of the dose during 5 hours 15 minutes) on Days 1 to 4, with carboplatin AUC 5 and PLD 30 mg/m² administered concurrently on Day 4 (treatment repeated every 28 days for up to six cycles).

Arm B (Control). Carboplatin AUC 5 and PLD 30 mg/m² administered on Day 1 of each 28-day cycle, repeated for up to six cycles.

Number of patients:

The trial will enroll up to a maximum of 400 patients with positive IHC staining for p53.

Diagnosis and main criteria for inclusion:

Inclusion criteria:

1. Archived sections from the original FFPE sample reviewed by a gynecological pathologist confirming High Grade Serous Ovarian Cancer, High Grade Serous Peritoneal Cancer or Primary Fallopian Tube Cancer, and positive IHC staining for p53 assessed according to defined standard (as detailed in the laboratory manual). Cases that do not show p53 staining will not be included.
2. Radiologically-confirmed Disease Progression between six and twenty-four (6-24) months after a first or second platinum based regimen.
3. At least a single (RECIST v1.1) measurable lesion.
4. Adequate organ function prior to registration:
 - a) Bone Marrow Reserve:
 - Absolute neutrophil count (ANC) $\geq 1.5 \times 10^9/L$,
 - Platelets $\geq 100 \times 10^9/L$,
 - Hemoglobin $\geq 9 \text{ g/dL}$.
 - b) Hepatic:
 - Total bilirubin level $< 1.5 \times \text{ULN}$,
 - ALT and AST $< 2.5 \times \text{ULN}$.
 - c) Renal:
 - Calculated creatinine clearance $> 30 \text{ mL/min}$.
 - d) Electrolytes
 - Potassium within institutional normal ranges.

5. Toxicities from previous cancer therapies, excluding alopecia, must have recovered to grade 1 (defined by CTCAE version 4.0). Chronic stable grade 2 peripheral neuropathy secondary to neurotoxicity from prior therapies may be considered on a case by case basis by the Principal Investigator.
6. If of childbearing potential, negative pre-treatment serum pregnancy test.
7. If of childbearing potential, willing to use an effective form of contraception (see below) during chemotherapy treatment and for at least six months thereafter.
Such methods include: (if using hormonal contraception this method must be supplemented with a barrier method, preferably male condom).
 - Combined (estrogen and progestogen containing) hormonal contraception associated with inhibition of ovulation:
 - Oral
 - Intravaginal
 - Transdermal
 - Progestogen-only hormonal contraception associated with inhibition of ovulation:
 - Oral
 - Injectable
 - Implantable
 - Intrauterine device (IUD)
 - Intrauterine hormone-releasing system (IUS)
 - Bilateral tubal occlusion
 - Vasectomized partner
 - True sexual abstinence when this is in line with the preferred and usual lifestyle of the patient. Periodic abstinence (e.g., calendar, ovulation, symptothermal, post-ovulation methods), declaration of abstinence for the duration of a trial, and withdrawal are not acceptable methods of contraception.
 - Male condom with spermicide (female condom and male condom should not be used together)
8. ECOG performance status of 0 to 1 (Appendix I).
9. ≥ 18 years of age.
10. Written informed consent obtained prior to any screening procedures and in accordance with federal, local, and institutional guidelines.
11. Patient has exhausted all available treatments, including surgery, and is considered a suitable candidate to receive carboplatin/PLD.

Exclusion criteria:

1. Prior exposure to cumulative doses of doxorubicin >400 mg/m² or epirubicin >720 mg/m².
2. Confirmed cardiac history of any of the following:
 - a) Myocardial infarct within six months prior to registration,
 - b) New York Heart Association Class II or worse heart failure (Appendix II),
 - c) A history of familial long QT syndrome,
 - d) Clinically significant pericardial disease,

- e) Electrocardiographic evidence of acute ischemia,
- f) Symptomatic atrial or ventricular arrhythmias not controlled by medications,
- g) QTc \geq 480 msec calculated from a single ECG reading or a mean of 3 ECG readings using Fridericia's correction (QTcF = QT/RR^{0.33}),
- h) Bradycardia (< 40bpm),
- i) Left ventricular ejection fraction (LVEF) < the institution lower limit of normal as assessed by ECHO.

[figure not shown]
3. Major abdominal surgery or peritonitis within six weeks prior to study treatment.
4. Unresolved bowel obstruction, sub-occlusive disease or the presence of brain metastases.
5. History of uncontrolled allergic reactions to carboplatin, platinum containing compounds or mannitol and/or hypersensitivity to PLD or to any of the excipients.
6. Unable to undergo imaging by either CT scan or MRI.
7. Evidence of any other medical conditions (such as psychiatric illness, infectious diseases, neurological conditions, physical examination or laboratory findings) that may interfere with the planned treatment, affect patient compliance or place the patient at high risk from treatment related complications.
8. Breast feeding.
9. Concurrent malignancy requiring therapy (excluding non-invasive carcinoma or carcinoma in situ).
10. Patients requiring or undergoing concurrent treatment with live vaccines.
11. Patients requiring or undergoing concurrent treatment with phenytoin.
12. Known HIV positive status, active hepatitis B or C status.
13. Is taking any concurrent (or within 4 week prior to registration) anti-cancer therapy, immunotherapy, radiotherapy or any ancillary anti-cancer therapy; or any therapy that is considered to be investigational (i.e., used for non-approved indications(s) and in the context of a research investigation). Supportive care measures are allowed.
14. Patients unable to be regularly followed for any reason (geographic, familiar, social, psychological, housed in an institution e.g., prison because of a court agreement or administrative order). Patients who are dependent on the sponsor/CRO or investigational site as well as on the Investigator.

Test product, dose and mode of administration:

Patients will receive a fixed dose of 4.5 g APR-246 (1.5 g of the dose during first 45 minutes followed by 3 g of the dose during 5 hours 15 minutes) if randomized to Arm A.

In all cycles, APR-246 will be administered as a 6-hour infusion daily for four consecutive days (Study Day 1 to Day 4). Carboplatin and PLD will be administered on Day 4 at the same time as the final infusion of APR-246. Carboplatin followed by PLD administration should commence 2-hours after the start of the APR-246 infusion.

Further administration of APR-246 (repeated in 28-day cycles) will commence three days prior to subsequent chemotherapy cycles, with the fourth dose administered the same day as the chemotherapy.

Duration of treatment:

Patients will receive up to six 28-day cycles of the carboplatin/PLD chemotherapy regimen with or without APR-246.

Reference therapy, dose and mode of administration:

Patients randomized to Arm B will not receive APR-246.

Carboplatin and PLD will be administered on Day 1 as per hospital practice. Cycles will be repeated every 28 days for up to six cycles.

Criteria for evaluation:

Efficacy: Patients with measurable disease will be assessed using RECIST (v1.1) criteria and GCIG CA-125 Criteria.

Safety: AEs will be collected throughout the study, from informed consent until 30 days after the last administration of study treatment. AEs will be graded according to NCI CTCAE version 4.0. Serious adverse events (SAEs) will be reported according to Directive 2001/20/EC and 2005/28/EC and the ICH GCP guidelines.

Sample size calculation:

The phase II portion of this study has a flexible sample size. The purpose is to use a smaller sample size with very small or very large observed effect sizes, and a larger sample size where observed effect sizes are promising but more data are needed. For small observed effect sizes (with typically smaller sample sizes), the study results will have traditional phase II interpretations. However, for moderate/large observed effect sizes (with potentially larger sample sizes), the design is intended to provide sufficient evidence to justify regulatory conditional approval.

LIST OF ABBREVIATIONS

AE	Adverse Event
ALP	Alkaline Phosphatase
ALT	Alanine Aminotransferase
AML	Acute Myeloid Leukemia
ANC	Absolute Neutrophil Count
APTT	Activated Partial Thromboplastin Time
AST	Aspartate Aminotransferase
AUC	Area Under the Curve
BICR	Blinded Independent Central Review
BW	Body weight
CA-125	Cancer Antigen 125
CD	Candidate Drug
CLL	Chronic Lymphocytic Leukemia
Cmax	Maximal Plasma Concentration
CNS	Central Nervous System
CR	Complete Response
CT	Computed Tomography
CTCAE	Common Terminology Criteria for Adverse Events
DILI	Drug-induced Liver Injury
DNA	Deoxyribonucleic acid
DSMB	Data and Safety Monitoring Board
ECG	Electrocardiogram
ECHO	Echocardiogram
ECOG	Eastern Cooperative Oncology Group
eCRF	Electronic Case Report Form
EOC	Epithelial Ovarian Cancer
FDA	U.S. Food and Drug Administration
FFPE	Formalin Fixed Paraffin Embedded
GCIG	Gynecologic Cancer Intergroup
GCP	Good Clinical Practice
GFR	Glomerular Filtration Rate
GMP	Good Manufacturing Practice
HIV	Human Immunodeficiency Virus
HGSOC	High Grade Serous Ovarian Cancer
HL	Hy's Law
HR	Hazard Ratio
IB	Investigator's Brochure
IC ₅₀	Inhibitory Concentration 50%
ICH	International Council for Harmonization
IDMC	Independent Data Monitoring Committee
IEC	Independent Ethics Committee

IHC	Immunohistochemistry
IMP	Investigational Medicinal Product
INR	International Normalized Ratio
IRB	Institutional Review Board
IUD	Intrauterine Device
IUS	Intrauterine Hormone-releasing System
IV	Intravenous
IWRS	Interactive Web Response System
LBM	Lean Body Mass
LD	Longest Diameter
LDH	Lactate Dehydrogenase
LVEF	Left Ventricular Ejection Fraction
MedDRA	Medical Dictionary for Regulatory Activities
MHRAUK	Medicine and Healthcare Products Regulatory Agency
MQ	Methylene Quinuclidinone
MRI	Magnetic Resonance Imaging
MUGA	Multi Gated Acquisition Scan
NCI	National Cancer Institute
NOAEL	No Observed Adverse Effect Level
OS	Overall Survival
PARP	Poly (adenosine diphosphate [ADP]) Ribose Polymerase
PD	Progressive Disease
PFI	Platinum-free Interval
PFS	Progression-free survival
PH2RD	Phase II Recommended Dose
PHL	Potential Hy's Law
PiSARRO	P53 Suppressor Activation in Recurrent High Grade Serous Ovarian Cancer
PLD	Pegylated Liposomal Doxorubicin
PPE	Palmar-Plantar Erythrodysesthesia
PPoS	Predicted Probability of Success
PR	Partial Response
PRIMA	p53 Reactivation and Induction of Massive Apoptosis
QoL	Quality of Life
RECIST	Response Evaluation Criteria In Solid Tumors
SAE	Serious Adverse Event
SaOS-2	Osteosarcoma Cell Line
SD	Stable Disease
TEAE	Treatment-emergent Adverse Event
Tid	Three Times Daily
ULN	Upper Limit of Normal
ULRR	Upper Limit of Response Range
US	United States
WBC	White Blood Cell Count

WHO World Health Organization
Wt Wild Type

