8.1.3 Target Lesions

All measurable lesions up to a maximum of two lesions per organ and five lesions in total, representative of all involved organs, should be identified as target lesions and recorded and measured at pre-treatment. Target lesions should be selected on the basis of their size (lesions with the longest diameter) and their suitability for accurate repeated measurements (either by imaging

techniques or clinically). A sum of the diameters (longest for non-nodal lesions, short axis for nodal lesions) for all target lesions will be calculated and reported as the pre-treatment sum diameters. The pre-treatment sum diameters will be used as reference by which to characterize the objective tumor response.

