9.5.2 Phase II Analysis

9.5.2.1 Primary analysis

At the final analysis (which occurs after 12 months of follow-up after the last patient is enrolled), a one-sided p-value is calculated for a stratified logrank test comparing treatment versus control. This corresponds to a formal test of the null hypothesis that the survival (event free) distribution of the treatment group is less than or equal to the survival distribution of the control group, i.e.

$$\begin{aligned} H_0: S_T(t) &\leq S_C(t) \\ H_a: S_T(t) &> S_C(t) \end{aligned}$$

where $S_T(t)$ and $S_C(t)$ are the survival distributions for the treatment and control groups, respectively, and $t > 0$ denotes observation time. The stratification factors for the test include

previous PFI (6-12, 12-24 months), BRCA status (known positive versus other) and prior lines of platinum-based treatment (1,2). The treatment will be considered superior to control if the corresponding one-sided p-value is less than or equal to 0.023. If the p-value is greater than 0.023 but less than 0.10, there may be sufficient promise to conduct another trial. The significance level of 0.023 is selected to control the overall Type I error of the adaptive design to be less than 0.025, as shown via simulation.

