9.8.4 Operating Characteristics

Complete operating characteristics (including power and Type I error) are provided in the Statistical Appendix (See Appendix V) for a variety of scenarios. In general the design has about 0.70 power for detecting a hazard ratio of 0.70 or smaller with one-sided Type I error less than 0.025.

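### The primary PFS logrank test is valid but leaves baseline ECOG and tumour size unused; prespecifying adjustment for them is a cheap efficiency gain

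*Combined protocol and SAP*

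**What the plan says.** The synopsis fixes the endpoint: "Progression-free survival (PFS) based on Blinded Independent Central Review (BICR) is the primary endpoint". Under Section 9.5.2.1, "a one-sided p-value is calculated for a stratified logrank test comparing treatment versus control". The strata are platinum-free interval (cut at 12 months), BRCA status (known positive or other) and prior platinum lines (one or two), the same factors as in Sections 6.3, 9.6 and 9.8.2. The decision rule is: "The treatment will be considered superior to control if the corresponding one-sided p-value is less than or equal to 0.023". Section 9.5.2.2 promises hazard ratios with 95% confidence intervals but names neither a model nor covariates. No covariate-adjusted PFS analysis is described anywhere.

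The baseline data stand as follows.
- **ECOG:** assessed pre-treatment (Section 7.2.2; Tables 9 and 10). Eligibility limits it to 0 or 1.
- **Tumour size:** under Section 8.1.3 a sum over all target lesions "will be calculated and reported as the pre-treatment sum diameters". Inclusion criterion 3 requires at least one measurable lesion, so every eligible patient should have a value.
- **CA-125:** Tables 9 and 10 have no mark in the pre-treatment column. The first sample is due on Cycle 1 Day 1 or up to three days before. Section 8.3.3.2 asks for a sample within two weeks before treatment. Section 9.7.3.2 uses CA-125 in the interim predictions and excludes it from the final analysis.

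On power, Section 9.8.4 says: "In general the design has about 0.70 power for detecting a hazard ratio of 0.70 or smaller".

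**The concern.** In a time-to-event analysis, prognostic variation left inside the strata pulls the hazard ratio that the test sees towards 1, even under perfect randomization. Some power is lost. A covariate-adjusted stratified logrank test recovers part of it: it removes from the logrank numerator the part predicted by chance covariate imbalance within strata and reduces the variance to match. The strata and the null hypothesis stay the same. Stated power is modest and the two main covariates are already on the case report form, so any gain needs no extra patients, scans or follow-up.

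**Working it through.** **1. The plan's own figure.** Appendix V is not in the public copy, so the 0.70 can be checked only for plausibility. For a single fixed analysis with 1:1 allocation:

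events = 4(z₀.₉₇₇ + z₀.₇₀)² / (ln 0.70)² = 4(1.995 + 0.524)² / 0.1272 ≈ 200 (Schoenfeld; 204 by Freedman). Power at 200 events is 0.701.

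The documents give no event target. The adaptive rules were therefore also simulated (2,000 runs per setting) with looks at 150 to 350 patients, Pr(HR<0.8)<0.30, PPoS>0.95 from 200 patients, and a final test 12 months after the last patient. Assumptions not in the plan: accrual rate, exponential PFS, no dropout, a normal approximation to the posterior and to PPoS, an unstratified test, and a small-effect stop counted as no success. The control medians of 9.4 and 11.3 months come from the background in Section 2.2 and are not stated design inputs. At HR 0.70:

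| Patients/month | Power |
|---|---|
| 5 | 0.71–0.73 |
| 10 | 0.65–0.66 |
| 15 | 0.60 |
| 20 | 0.55–0.59 |
| 30 | 0.48–0.53 |

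So 0.70 is plausible under slow accrual but cannot be confirmed. In the same settings a fixed 400-patient trial with the same unadjusted test had power 0.77–0.94, and the small-effect rule stopped 25–45% of trials.

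**2. Gain from adjustment.** The unknown input is the SD of the added covariates' contribution to the log hazard. Runs A and B compare the planned test with the covariate-adjusted stratified logrank test at one-sided 0.023. They assume conditional HR 0.70, 15 patients a month, control median 11.3 months, scans on the protocol calendar, analysis 12 months after the last patient and no interim stopping, with 1,500 trials per setting (Monte Carlo SE about 0.01).

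| Run | N | SD | Planned | Adjusted | Gain |
|---|---|---|---|---|---|
| A | 400 | 0 | 0.82 | 0.82 | 0.00 |
| A | 400 | 0.25 | 0.79 | 0.80 | 0.01 |
| A | 400 | 0.50 | 0.73 | 0.77 | 0.04 |
| A | 400 | 0.75 | 0.64 | 0.71 | 0.07 |
| B | 400 | 0 | 0.827 | 0.829 | 0.002 |
| B | 400 | 0.3 | 0.794 | 0.813 | 0.019 |
| B | 400 | 0.5 | 0.703 | 0.749 | 0.046 |
| B | 400 | 0.7 | 0.655 | 0.745 | 0.090 |
| B | 280 | 0 | 0.609 | 0.607 | −0.002 |
| B | 280 | 0.3 | 0.586 | 0.605 | 0.019 |
| B | 280 | 0.5 | 0.515 | 0.563 | 0.048 |
| B | 280 | 0.7 | 0.480 | 0.559 | 0.079 |

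Run A adjusted for platinum-free interval in months, ECOG and two correlated continuous covariates standing for tumour size and CA-125. A smaller covariate set has a smaller joint SD and should be read from a higher row.

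**3. Mechanism.** Run C (280 patients, 10 a month, eight strata, one baseline score, 1,500 trials) used a stratified Cox model. With the conditional HR held at 0.70, the average HR without the score moved from 0.693 (SD 0) to 0.722 (SD 0.5) and 0.742 (SD 0.7). With the score it was 0.694 at each. Power went from 0.695 to 0.694 (SD 0), 0.649 to 0.681 (SD 0.3) and 0.588 to 0.669 (SD 0.5). If the 0.70 in Section 9.8.4 is instead the HR that the unadjusted test sees, a lower conditional HR applies. Power then went from 0.676 to 0.710 (SD 0.3, conditional HR 0.685) and from 0.694 to 0.785 (SD 0.5, conditional HR 0.66). The gain is positive on either reading.

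**4. Type I error at HR 1, level 0.023 (SE about 0.004).** Run A: planned 0.018–0.025, adjusted 0.017–0.026. Run B: planned 0.019–0.025, adjusted 0.019–0.029. The highest value lies (0.029 − 0.023)/0.004 = 1.5 SE above 0.023. None of these runs includes the interim looks.

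**The case against.** The planned test is conventional and uses exactly the randomization factors; no bias or Type I error fault is shown. The size of the gain rests on a prognostic strength that the documents do not give, and ECOG has only two levels here. The power runs are not the adaptive design: with uninformative covariates Run A gives 0.82, not 0.70. The 0.023 level was calibrated by simulation for the unadjusted test, with only 0.002 to spare below 0.025. The interim model in Sections 9.7.1 and 9.7.2 has no covariates, so applying an adjusted test to its imputations would be incoherent. Tumour size also needs care: optional biopsies follow randomization, and Section 8.5.1 requires a biopsied lesion to be recorded as non-target, so the baseline sum could depend on a choice made after assignment is known.

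All of this stands as limits on the claim and on the fix. It does not remove the point: the simulations agree in direction, and with uninformative covariates there is no loss beyond simulation error.

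Two stronger readings are tempting. A reader might infer that CA-125 is a ready baseline covariate. The schedule does not support that: the Day 1 sample may follow open-label assignment, and Section 9.7.3.2 keeps CA-125 out of the final analysis. A reader might also infer that cutting the platinum-free interval at 12 months is what costs power. In Run A, adjusting for the interval in months alone gained nothing.

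**Conclusion.** The point holds as an efficiency improvement. Section 9.5.2.1 is valid but leaves ECOG and baseline tumour size unused. For the covariate-adjusted stratified logrank test the gain is about 0 points (no information), 1–2 points (SD 0.25–0.3) and 4–9 points (SD 0.5–0.75). This rests on assumed covariate strength, accrual and control median, with fixed sample size and no interim stopping.

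A reader might infer that the unused covariates are why power is only about 0.70. The documents do not show this, and the adaptive simulation points mainly to the small-effect rule: power is 0.77–0.94 at a fixed 400 patients with the same unadjusted test. That comparison counts every small-effect stop as no success, although Section 9.8.3.2 lets the sponsor keep following enrolled patients blinded until 12 months after the last enrolment.

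**What to change.** - In Section 9.5.2.1, prespecify a covariate-adjusted stratified logrank test with the same eight strata. Add ECOG (0/1) and the log sum of target diameters from the pre-randomization scan, and set missing values to the stratum mean. State whether the local or central reading supplies the sum.
- Add log CA-125 only if the value is taken before randomization. In that case, amend Section 9.7.3.2 to say that its exclusion applies to post-baseline CA-125.
- Use the same test in PPoS with the covariates added to the imputation model, and say which model feeds Pr(HR<0.8).
- Re-run the Appendix V simulations before the first interim at 150 patients, to confirm that 0.023 still keeps Type I error below 0.025.
- Report the hazard ratio from a Cox model with the same strata and covariates, and keep the plain stratified logrank test as a sensitivity analysis.

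The cost is SAP wording, an extended interim model and one re-simulation. Section 9.7.3.2 already says that the CA-125 model is not yet in the simulations, so some of that work is due anyway. The downsides are a less familiar test and a hazard ratio that is conditional on the covariates. If the sponsor keeps the plain logrank test as primary, the adjusted stratified Cox model should be prespecified as a supportive PFS analysis.
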